#### 4.3.3 **Subject Withdrawal**

It is planned to randomize approximately 78 subjects, with 39 subjects per indication (VLU or DFU), at up to 3 clinical sites for this study. See **Section 10.4**, for a discussion of sample size. Pls may choose to discontinue a subject's participation in the study if they believe it is in the subject's best interest clinically. The reason(s) for withdrawal must be recorded on the eCRF. If a subject is prematurely withdrawn from the study for any reason, the PI must make every effort (with proper documentation) to perform the evaluations described for the End of Study Visit. A subject may also be withdrawn from study by the sponsor or the IRB. Subjects who fail to qualify for enrollment during Screening Period will be considered Screen Failures and the reason for failure will be documented.

### 5 Study Agent/Interventions

### 5.1 Identity

Omeza® Products Bundle includes use of the following products (see **Appendix 1**) applied in the same manner as SOC for each indication VLU or DFU.

- Omeza® Lidocaine Lavage
- Omeza® Collagen Matrix
- Omeza® Skin Protectant

The lot numbers and expiration dates of the investigational products will be provided in the certificate of analysis and recorded in the eCRF and accountability log. A sample of

the label will be filed in the clinical site study files. All investigational TEST products will be prepared in accordance with current Good Manufacturing Practices (GMP).

Standard of Care (SOC): See **Appendix 2**: SOC for VLUs and **Appendix 3**: SOC for DFUs

### 5.2 Packaging

Each kit of investigational products will be labeled with the following information:

恭	PRODUCT BUND	DIF
OMEZA	Artwork# 2019-PB-B	
Protocol #: 100	Subject Randomiza	tion/Kit #:
Subject	's Initials #:	
	Each Kit Contain	s:
	[1] 2ml vial Omeza Lidoca	aine Lavage
[1] 2ml vial Omeza Collagen Matrix		
	(1) 2ml vial Omeza Skin P	Protectant
	INVESTIGATIONAL PRO	DDUCT
For T	opical Use Only. Keep out of	f reach of children.
	Store kit between 68°	F - 77°F
CAUTION: Investiga	ational product - Limited by	U.S. law to investigational use.
Manufactured for: OMEZA, I	LLC. USA	Sarasota, FL 34236

TEST product kits will be supplied to the clinical sites by Omeza, LLC. Each kit will contain one 2 mL vial of Omeza® Lidocaine Lavage, one 2 mL vial of Omeza® Collagen Matrix and one 2 mL vial of Omeza® Skin Protectant.

### 5.3 Storage

Supplies of the TEST products should be stored at room temperature 20° to 25°C (68° to 77°F); excursions permitted to 15° to 30° C (59° to 86° F) [see USP controlled room temperature]. Do not freeze.

The PI, or qualified designee, is responsible for the proper storage of the study products according to the manufacturer's recommendations and all applicable Federal/State regulatory guidelines.

### 5.4 Dosage and Administration of Study Agent

At each treatment visit (Weeks 1 through Week 12), each subject will undergo the wound care procedure as outline in the assigned randomized treatment i.e. either the Omeza® Products Bundle (TEST) or the standard of care (SOC). In all cases each treatment will be applied according to the diagnosed indication. If the wound closes before Week 12, the subject will continue to come in for all the remaining study visits until study completion, but the TEST subjects will be treated with the Omeza® Skin Protectant only.

The TEST treatment will be labeled with a subject's unique randomization number, (which is also the kit number). In addition, the visit number will be hand-written on the label at the site. The adhesive label will be placed on the subject's chart (source) and documented in the eCRF.

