### 3.2 Study Endpoints

#### Primary Endpoint:

- 1. Percent Change from Baseline in target wound measure at Week 4, Week 8 and by Week 12.
- 2. Ulcer Size Closure rate at Week 4, Week 8 and by Week 12.
- 3. Time to maximum closure or complete closure.
- 4. Incidence of DFU and VLU healing at Week 12.

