#### 6.2 Treatment Visit Week 1/Randomization/Baseline

Subjects will return for review of eligibility, baseline assessments, randomization and initiation of assigned treatment:

- Review of inclusion/exclusion criteria
- Subject to complete Baseline Wound-QoL questionnaire
- Concomitant medications
- Adverse event monitoring
- Wound examination
- Vascular assessment
- Target wound measurement and photography
- Randomization
- Wound Care, including the application of treatment (either TEST or SOC depending on randomization assignment see Appendices 2-4 for method)
- Schedule Treatment Visit Week 2

#### 6.3 Treatment Visits Week 2 - Week 11

Subjects will return to the study site once a week for a total of 11 Treatment Visits. These visits will include wound care and follow-up assessments. Every attempt will be made to schedule each Treatment Visit within the study day window of 7 days +/- 1 day, to assure proper wound care.

- Concomitant medications
- Adverse event monitoring
- Wound examination
- Vascular assessment
- Target wound measurement and photography
- Wound Care, including the application of treatment (either TEST or SOC depending as randomization assignment)
- Schedule the next weekly treatment visit

Note: If the wound closes before Week 12, the subject will continue to come in for all the remaining study visits until study completion, but the TEST subjects will be treated with the Omeza® Skin Protectant only.

### 6.4 End of Study Visit/ Treatment Visit Week 12

Subjects will return to the study site for the End of Study Visit on Week 12. If the wound has not closed by Week 12, the subject will be immediately excited from the study and no further follow-up will occur as part of the study.

- Routine laboratory evaluations
- Subject to complete end of Study Wound-QoL questionnaire
- Concomitant medications
- Adverse event monitoring
- Wound examination
- Vascular assessment
- Target wound measurement and photography
- Wound Care, including the application of treatment (either TEST or SOC depending on randomization assignment)

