## Appendix B. Schedule of Study Procedures/Evaluations

Period	Screening	Treatment		
Duration (Window)	1 week	12 weeks		
Visit	Screening (Day -7 +/-1 day)	Treatment Visit Week 1 Randomization/ Baseline	Treatment Visit Week 2,3,4,5,6,7,8,9,10,11# (7 days apart +/-1 day)	Treatment Visit Week 12 End of Study Visit ## (+/-1 day)
Visit Number	1	2	3-11	13
Informed Consent Form/HIPAA Authorization	Х			
Demographics (including Fitzpatrick Skin Type)	Х			
PE (All systems) / Vital Signs	Х			
Medical History	Х			
Urine Pregnancy Test**	Х			
Concomitant Medications	Х	Х	Х	X
Study Eligibility (I/E)	Х	Х		
Labs	Х			Х
Wound QoL Questionnaire		Х		Х
Randomization		Х		
Target Wound Identification	Х			
Vascular Assessment	Х	Х	Х	X
Wound Examination	Х	X	Х	Χ
Target Wound Measure and Photography	Х	Х	Х	Х
Ulcer Care Treatment Applied as Randomized		Х	Х	Х
Safety Assessments/Adverse Events/Intercurrent Illnesses		Х	Х	Х

\*\* Pregnancy testing is for females of childbearing potential

# If wound closes before Week 12, the subject will continue to come in for all the remaining study visits until study completion, but the TEST subjects will be treated with the Omeza® Skin Protectant only.

## If wound does not close by Week 12, the subject will be immediately exited from the study and no further follow-up will occur as part of the study.

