## Appendix 4: Omeza® Products Bundle Instructions

### Venous Leg Ulcer

- 1) Apply Omeza® Lidocaine Lavage and after 5 minutes wipe out debris
- 2) Perform appropriate sharp debridement as indicated
- 3) Apply additional Omeza® Lidocaine Lavage and wipe out debris
- 4) Apply Omeza® Collagen Matrix as primary dressing
- 5) Apply Omeza® Skin Protectant on periwound and surrounding intact skin from knee to toes
- 6) Apply foam as secondary dressing
- 7) Soft roll and compressive wrap (Dynaflex™ or Profore or any other preferred multi-layer compression bandage system)

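### Post-closure care is specified for the TEST arm only, and the protocol does not say whether compression or offloading continues in either arm, so the Week 12 healing comparison is open to bias

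*Protocol*

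**What the plan says.** Section 5.4 opens with a rule for both arms: "At each treatment visit (Weeks 1 through Week 12), each subject will undergo the wound care procedure as outline in the assigned randomized treatment". Section 5.5 repeats that care follows the randomized group at each treatment visit, with no exception for a closed wound.

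Section 5.4 then sets an exception for early closure. Subjects keep attending "until study completion, but the TEST subjects will be treated with the Omeza ® Skin Protectant only". The note in Section 6.3 says the same, and so does the footnote to Appendix B, which begins "If wound closes before Week 12, the subject will continue to come in for all the remaining study visits". None of the three gives a corresponding instruction for SOC.

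The treatment lists are in Appendices 2 to 4. In Appendix 4 the Skin Protectant is step 5 and foam is step 6. The last step is "Soft roll and compressive wrap" for VLU, or offloading for DFU. Appendices 2 and 3 (SOC) list collagen alginate, then foam, and end with the same compression or offloading element.

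Section 3.2 lists "Incidence of DFU and VLU healing at Week 12" among the primary endpoints, and Section 10.2 compares the proportion healed at that time. Section 3.1 has the target wound measured and photographed at all 13 visits.

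**The concern.** Compression and offloading are background care that the two arms are meant to share. If they continue after closure in one arm and stop in the other, whether an ulcer is still closed at Week 12 depends on the aftercare rule as well as on the product. The protocol states an aftercare rule for one arm, leaves the other arm to a general rule that does not mention closure, and does not say what happens to the shared components. The trial is open label, each site holds the randomization schedule (Section 4.3.2), and up to 3 sites may read the sentence differently. A listed primary endpoint is exposed: the proportion healed at Week 12. The Week 12 percent change is exposed to a lesser extent, because a reopened ulcer may be small relative to baseline.

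**Working it through.** **The plan's own figure.** The protocol gives no number for aftercare, closure or reopening. Its one quantitative claim is over 80% power for percent change, and it reproduces: 14 / (20 × √(1/26 + 1/52)) = 14 / 4.80 = 2.91, and Φ(2.91 − 1.96) = 83.0% (82.1% with the t distribution). That figure does not bear on this point. It is shown only to confirm the arm sizes of 52 TEST and 26 SOC, or 26 and 13 within each indication.

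**What each reading implies after closure.** The Section 5.4 default is applied to SOC in the same way in both rows.

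| Reading of the exception | TEST, closed ulcer | SOC, closed ulcer | Does background care differ by arm? |
|---|---|---|---|
| Literal: the Skin Protectant and nothing else | No foam; no compression (VLU) or offloading (DFU) | Full Appendix 2 or 3 list under the default | Yes |
| Of the three Omeza products, the Skin Protectant alone | Foam and compression or offloading may continue; not stated | Full Appendix 2 or 3 list under the default; closure not addressed | Not necessarily |

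The literal reading is available because Appendix 4 makes compression and offloading separate steps from the Skin Protectant. The second is available because the sentence can be taken to concern the study products alone. The protocol does not choose between them.

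**Weight of one reopened ulcer in the Week 12 healed proportion.**
- TEST: 1/52 = 1.9 points.
- SOC: 1/26 = 3.8 points.
- SOC within one indication: 1/13 = 7.7 points.

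**Illustration of a shift caused by aftercare alone.** All rates here are assumptions. Let a proportion p close before Week 12 in both arms (no true difference), and let reopening before Week 12 be r_S in SOC and r_T in TEST. The healed proportion at Week 12 is p(1 − r), so the spurious TEST minus SOC difference is p(r_S − r_T). With r_S = 5%:

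| p | r_T = 5% | r_T = 15% | r_T = 25% |
|---|---|---|---|
| 40% | 0 | 0.34 − 0.38 = −4 points | 0.30 − 0.38 = −8 points |
| 60% | 0 | 0.51 − 0.57 = −6 points | 0.45 − 0.57 = −12 points |

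These scenarios assume more reopening in TEST, so the shift runs against TEST. Exchanging r_S and r_T reverses the sign. If reopening is equal, there is no shift.

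**Which endpoints are exposed.** The proportion healed is taken at Week 12 among subjects who remain in the study after closure, so it is exposed directly. Percent change is exposed where it uses the Week 12 measurement, and at Weeks 4 and 8 only for ulcers already closed by then. Time to complete closure runs from start of treatment (Section 10.2). If first closure is the event, care given afterwards does not affect it.

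**The case against.** The strongest counter-argument is that the second reading is the more natural one. Sections 1.2 and 5.1 define the bundle as three products, and the kit in Section 5.2 contains those three vials and nothing else. Section 9.9 lists foam, soft roll and compressive wrap under standard of care, separately from the Omeza devices. Section 3.1 has standard of care billed for both arms, and Section 5.1 says the products are applied in the same manner as SOC. The exception itself sits in a section on the study agent. On this reading compression and offloading could continue in both arms, and no sentence in the protocol withdraws them from TEST.

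This stands as far as it goes. A reader might infer that compression and offloading do differ by arm, or that they differ whichever way the sentence is read. The documents support neither. The first is one reading of an ambiguous sentence. The second fails because, with the default applied to SOC in the same way throughout, the second reading allows equal background care.

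A reader might also infer that the Week 12 results are biased and cannot be repaired. That too is more than the documents show. No reopening rate is given, and the weekly measurements make first closure and reopening observable, so their influence can be examined.

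The objection does not remove the inconsistency. Appendix 4 presents foam, compression and offloading as numbered steps of the TEST procedure, the exception says only one item is used, and the text nowhere says that the other steps continue. Later analysis can describe the consequence, but it cannot make aftercare comparable once it has been delivered.

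**Conclusion.** The point holds as an inconsistency that leaves an endpoint open to bias, not as a demonstrated bias. A post-closure regimen is stated three times for TEST and never for SOC. It departs from the default in the same section, and the protocol does not say whether the shared components continue in either arm. The Week 12 proportion healed is the endpoint most exposed.

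The size and direction cannot be derived from the documents. The illustrative shifts of 0 to 12 points rest wholly on assumed closure of 40% or 60% and assumed reopening of 5% to 25%. If all sites continue background care equally in both arms, this source of bias disappears. The correction is worth making because it is cheap and must be made before care is delivered, but the point ranks below a must-fix.

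**What to change.** Reconcile Sections 5.4, 5.5 and 6.3 and the Appendix B footnote with Appendices 2 to 4. The revised text should:
- state post-closure care for both arms;
- say explicitly whether foam and compression or offloading continue after closure;
- put those background components on a basis that does not depend on arm within each indication.

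What that care should be is a clinical decision for the sponsor, and this review takes no position on it.

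Record the date of first closure and any reopening in both arms, taken from the weekly measurements and photographs already scheduled, so that healing at Week 12 can be read alongside first closure.

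The cost is protocol wording and a small addition to the eCRF. No extra visits are needed, because subjects with closed ulcers already attend through Week 12.

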### 5.5 Accountability

The PI, or qualified designee, will dispense the study product only to randomized subjects during the study visits described in this protocol. At each treatment visit, each subject will undergo wound care corresponding to the treatment group to which they were randomized. The subject's unique randomization number, subject's initials, visit number and date of treatment will be written on the TEST product label and documented in the eCRF at the clinical site.

The PI, or qualified designee, will maintain an accurate inventory in the form of study product accountability logs beginning with recording the receipt of the study product as shipped by the sponsor (or designee) and the date received. In addition, accurate records of study product applied to subjects will be kept by the PI, or qualified designee, specifying the kit number, the subject number, and the date applied, for the subject and the master product accountability logs for the overall study. At the completion of the study, the PI will provide copies of this accountability log to the sponsor. At the completion of the study, following full accountability and reconciliation of all investigational product supplies, all unused/partially used investigational product kits will be returned and/or destroyed in accordance with the sponsor's (or designee's) written instructions. The PI must verify the accuracy of the accountability logs, and that no remaining supplies are in the PI's possession.

#### 5.5.1 **Subject Compliance with Study Agent**

Subjects will be considered treatment compliant, if the % compliance is calculated to be between 80% and 120%. Compliance will be calculated, as follows: % Compliance = (# study treatments divided by # the number of treatments that should have taken place based on the number of days the subject was in the trial) x 100. Compliance will be summarized "as treated".

#### 5.6 Concomitant Medications

All concomitant prescription medications, over-the-counter medications and non-prescription medications taken at the start of and during study participation will be reported on the eCRF. The following information must be recorded in the eCRF for each concomitant medication: generic name, route of administration, start date, stop date, dosage, and indication. Any changes in the dose or regimen of a concomitant medication must also be recorded in the eCRF. At the Screening Visit, subjects will be asked what medications they have taken during the last 30 days. Concomitant medications will be summarized "as treated".

#### 5.7 Prohibited Medications and Treatments

The following are medications that are prohibited at enrollment, during screening, and during the course of the study unless discussed with and approved by the medical monitor:

History of treatment 28 days prior to enrolment with immunosuppressants including:

systemic corticosteroids >10 mg daily dose,

- autoimmune therapy,
- hydroxyurea,
- application of topical steroids to the ulcer surface within 1 month prior to Screening Visit,

OR

Radiation therapy to the leg or foot, or chemotherapy within the last 12 months

OR

Skin ulcer previously treated within the last 4 weeks with biologic therapies e.g. cell therapy, growth factors

OR

Receive above medications during the screening period

OR

Are anticipated to require above medications during the course of the study

OR

Target wound has received wound dressings that include:

- growth factors
- engineered tissues
- skin substitutes (e.g., Apligraf, PriMatrix, AMNIOEXCEL (first generation), Regranex, Dermagraft, EpiFix, GraftJacket, OASIS, Omnigraft, or Integra BMWD)

#### 5.8 Permitted Concomitant Medications

Other than the medications listed above in **Section 5.7**, all medication will be permitted provided that the subject has been on a stable dose for at least one month prior to the Screening period and/ or the medical monitor agrees.

### 6 Study Schedule

The study will be conducted in 13 visits (see **Appendix B**)

### 6.1 Screening Visit (Day 0)

Seven (7) days prior to baseline and initiation of study treatment, subjects will present for a screening visit where they will undergo the following procedures:

- Informed consent process/HIPAA authorization
- Review of inclusion/exclusion criteria
- Medical history / Concomitant medications
- Demographic information (include Fitzpatrick Skin Type see Appendix 8)

 If female, document subject confirmed lack of pregnancy (for women of childbearing potential)

- Routine laboratory evaluations (see details in Section 7.1.4)
- Physical exam (All systems) and vital signs
- Target wound identification and wound examination
- Vascular assessment (see Appendix 6A)
- Target wound measurement and photography (see **Appendix 6B**)
- · Assignment of unique subject screening number
- Schedule Treatment Visit Week 1

#### 6.2 Treatment Visit Week 1/Randomization/Baseline

Subjects will return for review of eligibility, baseline assessments, randomization and initiation of assigned treatment:

- Review of inclusion/exclusion criteria
- Subject to complete Baseline Wound-QoL questionnaire
- Concomitant medications
- Adverse event monitoring
- Wound examination
- Vascular assessment
- Target wound measurement and photography
- Randomization
- Wound Care, including the application of treatment (either TEST or SOC depending on randomization assignment see Appendices 2-4 for method)
- Schedule Treatment Visit Week 2

#### 6.3 Treatment Visits Week 2 - Week 11

Subjects will return to the study site once a week for a total of 11 Treatment Visits. These visits will include wound care and follow-up assessments. Every attempt will be made to schedule each Treatment Visit within the study day window of 7 days +/- 1 day, to assure proper wound care.

- Concomitant medications
- Adverse event monitoring
- Wound examination
- Vascular assessment
- Target wound measurement and photography
- Wound Care, including the application of treatment (either TEST or SOC depending as randomization assignment)
- Schedule the next weekly treatment visit

Note: If the wound closes before Week 12, the subject will continue to come in for all the remaining study visits until study completion, but the TEST subjects will be treated with the Omeza® Skin Protectant only.

### 6.4 End of Study Visit/ Treatment Visit Week 12

Subjects will return to the study site for the End of Study Visit on Week 12. If the wound has not closed by Week 12, the subject will be immediately excited from the study and no further follow-up will occur as part of the study.

- Routine laboratory evaluations
- Subject to complete end of Study Wound-QoL questionnaire
- Concomitant medications
- Adverse event monitoring
- Wound examination
- Vascular assessment
- Target wound measurement and photography
- Wound Care, including the application of treatment (either TEST or SOC depending on randomization assignment)

### 6.5 Early Termination Visit

Subjects who no longer wish to participate in the study or who become ineligible to participate will be asked to return for final assessments (End of Study Visit).

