- 16. Osteomyelitis or bone infection of the affected foot as verified by x-ray within 30 days prior to randomization. (In the event of an ambiguous diagnosis, the subject will not be enrolled)
- 17. Suspected or confirmed gangrene or wound infection of the study ulcer, as evidenced by tissue necrosis, redness, pain, and/or purulent drainage and/or receiving systemic antibiotics for the treatment of such
- 18. History of immunodeficiency or any illness or condition, other than diabetes, that could interfere with wound healing e.g., excessive lymphedema, end-stage renal disease, severe malnutrition, liver disease, aplastic anemia, Raynaud's Syndrome, connective tissue disorder, acquired immune deficiency syndrome, HIV positive, or sickle cell anemia
- Subject has unstable Charcot foot or Charcot with bone exposed that could inhibit wound healing

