#### 9.4 Reporting Procedures

Any AE that meets the criteria for serious outlined in the protocol must be reported to the Medical Monitor within 24 hours from the time site personnel becomes aware of the event. The Medical Monitor Contact Information is:

Medical Monitor [name]

Palm Beach CRO [name] [contact] SAE Fax Line: [contact]

[contact]

Email: [contact]

A written report must be submitted and should consist of the Serious Adverse Event Report Form, accompanied by the following eCRF pages: demographics, medical history AEs, and concomitant medications. If the subject is hospitalized because of or during the course of an SAE, then a copy of the hospital discharge summary *with identifying information removed* should be faxed to SAE Fax line at [contact] or scanned and e-mailed to **[name]**, **MD to** [contact] and/or [name] at: [contact] as soon as it becomes available.

Withdrawal from the study and all therapeutic measures will be at the discretion of the PI, sub-investigator or medical monitor. All SAEs (related or with an unknown relationship to the study TEST product) will be followed until satisfactory resolution or until the PI or sub-investigator deems the event to be chronic or the subject to be stable. All SAEs will be recorded from signing of ICF until the end of the study.

Serious AEs occurring after the end of the study and coming to the attention of the PI must be reported only if they are considered (in the opinion of the PI) causally related to the study TEST product. After receipt of the initial report, the Medical Monitor will review the information and, if necessary, contact the PI, to obtain further information for assessment of the event. The Sponsor or their designated representative will be responsible for all information processing and reporting according to local legal requirements.

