### 9.7 Early Withdrawal of a Subject

If a subject is prematurely withdrawn from the study for any reason, the PI should record the reason(s) for withdrawal and make every effort to perform the evaluations described for the end of study visit.

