## 9.8 Replacement of a Subject Who Discontinues Study Treatment

Subjects who met entry criteria and have been randomized will not be replaced if they drop out from the study for any reason.

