# 10 Statistical Considerations (See Statistical Analysis Plan [SAP])

### 10.1 General Considerations and Populations

The primary endpoint is percent change from baseline in target wound measure by Week 12/End of Study.

All statistical testing will be performed at a two-sided alpha=0.05 level of significance. A detailed Statistical Analysis Plan (SAP) will be finalized prior to database lock.

All subjects who are randomized and receive at least one study treatment will be included in the Safety Population. All summaries of safety data will be based on this population and reported "as treated" – in case there are subjects that were not treated as per the randomization outcome.

All subjects who are randomized, receive at least one study treatment and have at least one post-baseline measure assessment will be included in the Intent-to-Treat Population (ITT). All efficacy summaries will be based on this population and will be reported according to the intent to treat principle (as randomized).

A review of major protocol violations will be performed. Major violations will include, but not be limited to, an assessment of compliance, use of concomitant medications and intercurrent illnesses. Subjects and data points without major protocol violations will be included as part of the Per-Protocol Population. If fewer than 10% of the subjects have major protocol violations, these analyses may not be performed.

All analyses and summaries will be reported overall and for each indication (venous leg ulcers and diabetic foot ulcers).

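### After early exit or undefined post-randomization ineligibility the protocol provides one final visit and no further wound measurement, so Week 12 values may be lost in relation to wound course

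*Protocol*

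**What the plan says.** **Exit.** Section 6.5 (Early Termination Visit) brings back subjects who no longer wish to participate, and those "who become ineligible to participate will be asked to return for final assessments (End of Study Visit"). Section 4.3.3 asks the investigator, for any premature withdrawal, "to perform the evaluations described for the End of Study Visit". Section 9.7 repeats the rule: "make every effort to perform the evaluations described for the end of study visit". The End of Study Visit in Section 6.4 includes target wound measurement and photography. None of these sections schedules a measurement after that visit.

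**Who may withdraw a subject.** Section 4.3.3 lets the investigator end participation in the subject's clinical interest and adds: "A subject may also be withdrawn from study by the sponsor or the IRB". Section 9.4, on reporting of serious adverse events, states: "Withdrawal from the study and all therapeutic measures will be at the discretion of the PI, sub-investigator or medical monitor".

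**Stopping treatment.** Section 9.8 has a heading about a subject who discontinues study treatment. Its text reads: "Subjects who met entry criteria and have been randomized will not be replaced if they drop out from the study for any reason".

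**Entry criteria.** Both exclusion lists in Section 4.2 contain "Suspected or confirmed gangrene or wound infection of the study ulcer" (VLU 19, DFU 17).

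**Early closure.** Under Sections 3.1 and 6.3, a subject whose wound closes before Week 12 attends all remaining visits.

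**Analysis.** Section 10.1 names percent change in wound measure by Week 12/End of Study as the primary endpoint. It says that efficacy summaries "will be reported according to the intent to treat principle (as randomized"). Section 10.2 specifies an MMRM and also compares the proportion healed at Week 12.

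**The concern.** Follow-up to Week 12 is guaranteed for wounds that close early but not for subjects who leave or are judged ineligible. Section 6.5 must concern people already in the study, because screen failures are handled in Section 4.3.3 and ineligibility found at Week 1 in Section 3.1. It does not say what makes a randomized subject ineligible. The only definition to hand is the entry criteria, and some of these can arise on study and mark a poor wound course: infection or gangrene of the ulcer, systemic antibiotics for it, or need for an interfering treatment.

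The study is open label, the site holds the allocation schedule (Section 4.3.2), and the wound is measured weekly. A decision that ends follow-up can therefore be made knowing both the arm and the wound's course. If such exits differ between arms, the Week 12 contrast no longer compares the groups as randomized. A SAP cannot repair this, because it cannot recover measurements that were never taken.

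**Working it through.** **1. The sections side by side**

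| Situation after randomization | Wound measured afterwards? | Where |
|---|---|---|
| Wound closes early | Yes, at all visits to Week 12 | 3.1, 6.3 |
| Subject no longer wishes to participate | One exit visit | 6.5 |
| Subject becomes ineligible (undefined) | One exit visit | 6.5 |
| Withdrawn for any reason | One exit visit | 4.3.3, 9.7 |
| Stops assigned treatment, remains willing | Not stated | 9.8 heading only |

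The last row is the gap. The heading of 9.8 names this subject, but its text speaks only of dropping out of the study.

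**2. The benchmark**

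Section 10.4 gives 78 subjects randomized 2:1 (52 TEST, 26 SOC), a difference of 14 units, SD 20 and two-sided alpha 5%.

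- Standard error = 20 × √(1/26 + 1/52) = 4.80.
- 14 / 4.80 = 2.91, and 2.91 − 1.96 = 0.95, so power is 0.83 (0.82 with the noncentral t).

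The stated figure of over 80% is reproduced, and 14 units is the yardstick below.

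**3. Illustration of the shift (assumptions, not estimates)**

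Let a share f of an arm be removed. Suppose those removed would have had g units less wound reduction at Week 12 than those retained. The mean reduction among retained subjects then exceeds the true arm mean by f × g. In a comparison of observed Week 12 values:

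shift in TEST minus SOC = g × (f_TEST − f_SOC), where a positive value favours TEST.

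With g = 40 units:

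| Removed, TEST vs SOC | Shift (units) | Share of the 14 units |
|---|---|---|
| 10% vs 10% | 40 × 0.00 = 0 | 0% |
| 20% vs 10% | 40 × 0.10 = 4 | 29% |
| 10% vs 20% | 40 × (−0.10) = −4 | 29%, against TEST |
| 25% vs 5% | 40 × 0.20 = 8 | 57% |

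**4. Is the assumed gap compatible with SD 20?**

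A split into removed and retained subjects contributes variance f(1 − f)g², which cannot exceed 20² = 400.

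- f = 0.20, g = 40: 0.16 × 1600 = 256, compatible.
- f = 0.25, g = 40: 0.1875 × 1600 = 300, compatible.
- At f = 0.20 the largest possible gap is 20/√0.16 = 50 units, so one arm's mean can shift by at most 0.20 × 50 = 10 units.

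**5. What the illustration leaves out**

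It describes observed Week 12 values, not the planned MMRM, which also uses each subject's earlier visits and the exit measurement. The protocol gives no dropout or removal rate, so no actual bias can be computed.

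**The case against.** The strongest reply is that the protocol does not order the removal of failing wounds, and several sections point the other way. Four stronger readings are tempting, and the documents do not support them.

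- **That stopping the product ends participation.** No section says so. Section 10.3 lists subjects who discontinue product because of adverse events without linking this to leaving the study. The supportable defect is that the two are not separated.
- **That entry criteria act as exit triggers throughout.** Appendix B and Sections 6.1 to 6.4 place eligibility review only at Screening and Week 1. ABI is repeated at every visit, but nothing tests it against the entry limits after baseline. Section 5.7 lets the medical monitor approve otherwise prohibited treatments. Section 10.1 handles concomitant medications and intercurrent illness as Per-Protocol matters, which suggests that some such subjects stay on study.
- **That Section 9.4 gives a general power to remove slow-healing wounds.** Its sentence on withdrawal belongs to serious adverse event reporting.
- **That a large bias can be computed from one arm.** A reader might assume that 5 of 52 TEST subjects leave with a change of +20% against −60% in those retained, and obtain 0.096 × 80 = 7.7 units. That is a shift in one arm's observed mean, not in the treatment difference under MMRM. It also implies a between-group variance of 0.096 × 0.904 × 6400, about 556 (SD 23.6), which already exceeds the protocol's SD of 20.

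It is also fair to say that the exit visit measures the wound, that worsening recorded before exit enters the MMRM, and that the wording by Week 12/End of Study may let the exit value count.

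What stands is narrower. The exit rule appears in three sections, post-randomization ineligibility is undefined, and nothing measures the wound after exit. An exit value used for Week 12 is an earlier value in its place. MMRM relies on missing at random, which is doubtful if removal depends on clinical judgement or planned therapy that earlier wound sizes do not capture.

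**Conclusion.** The point holds as a gap in data collection. Sections 4.3.3, 6.5 and 9.7 end measurement at exit, Section 6.5 applies this to an undefined class of ineligible subjects, and Section 9.8 leaves no stated place for someone off treatment but on study. Subjects with a poor wound course may therefore lose their Week 12 value through decisions made with the arm known. That weakens the as-randomized comparison in Section 10.1. That failing wounds are the ones lost is an inference from the entry criteria and the discretion allowed; it is not stated in the protocol.

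The direction and size of bias are unknown. They depend on whether removal differs between arms and on how much the MMRM recovers. Under an assumed 40-unit gap, removal of 20% against 10% shifts an observed-value comparison by 4 of the 14 design units, in either direction; equal removal with equal gaps shifts it by none. The change is worth making because it is cheap and the lost data cannot be recovered later.

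**What to change.** Amend Sections 4.3.3, 6.5 and 9.7, and reconcile them with 9.8:

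- Separate stopping assigned treatment from withdrawing from the study.
- State that meeting an entry exclusion after randomization, stopping assigned treatment or starting another wound therapy does not by itself end data collection.
- Continue the already scheduled wound measurement and photography to Week 12, unless the subject withdraws consent or the investigator judges that further visits are not in the subject's interest.
- Record the start date of any other wound therapy.
- Include these measurements in the as-randomized analysis.

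Clinical decisions on stopping or changing treatment, and the existing authority to withdraw a subject, stay as they are. The cost is amendment wording and visits, for a few subjects, that are already in the schedule. The small downside is that some later measurements will reflect other therapies; the recorded start dates allow this to be examined.
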